Follow-up: After participant allocation, telephonic follow up will be made during both periods of the trial with a frequency that is dependent on the intervention group of the patient in that period. Participants in the HBE group will be called weekly for 2 weeks, and then will be called biweekly for a month, until each period of 6 weeks has ended. In contrast, patients in the control group will be called every three weeks along each period. With the purpose of verifying both HBE adherence and correct use of wooden prisms, every participant will be asked to send a photograph of the bed head legs during the follow-up telephone call. The photograph will be received by the researcher via e-mail or smartphone and will be encoded and saved in a hard disk. At the end of the first period, RDQ and SF-36 questionnaires will be applied and researchers will store the returned prisms during washout period. When washout period has ended, RDQ and SF-36 questionnaires will be applied again in order to be sure of the absence of any carry-over effect in the group initially allocated to HBE. Finally at week 14, RDQ, SF-36 and Patient Preference questionnaires will be administered to complete study ending outcome assessments.

In figure 5, a schematic representation of follow-up is shown.

[figure not shown]

Figure 5: Schematic representation of photographic and telephonic follow-up. W1-6: Weeks from 1st to 6th in each period.

Primary outcome:

1. Effectiveness: Change of ≥ 0,6 points between basal RDQ questionnaire and the same questionnaire administered after 6 weeks of HBE use.

Secondary outcomes:

- 1. Quality of life: Change of ≥ 10 percentage points between basal SF-36 questionnaire and the same questionnaire administered after 6 weeks of HBE use.
- **2. Patient preference:** Proportion of patients who preferred HBE, after finishing 14 weeks of the study.
- 3. Safety: Proportion of patients with any reported adverse event during HBE or without bed inclination.

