between periods will be transformed into a binomial variable and a McNemar marginal homogeneity test will be applied. McNemar mid-p was used if discordant pairs sum was smaller than 25²⁸. Differences with one-tail p<0,05 will be accepted as statistically significant. Exploratory subgroup analysis will search for differences stratified according to age group, sex, ethnic group, BMI, comorbidities, cups of coffee per day, pharmacological adherence, and length and severity of symptoms; among other 16 baseline variables. Subgroup interactions will be tested with Chi-square or Fisher exact test, and effect size was expressed as a univariate relative risk from a generalized linear model of binomial family. As part of internal quality control of the clinical trial, a pre-test was applied to prove the assumption of a negligible *carry-over* effect, according to expert guidelines²⁹. Analysis of variance (ANOVA) for crossover studies was used in search for significant sequence, period and treatment effects, assuming a negligible *carry-over* effect. In the modified intention to treat analysis, participants with protocol violations because of bad adherence to HBE, were included, but it was not possible to include patients who withdrew from the study because outcome information could not be gathered completely.

Methodology diagram: A schematic representation of the trial methodology is presented in figure 6.

[figure not shown]

Figure 6: Schematic representation of the trial methodology. RDQ: Reflux Disease Questionnaire; SF-36: Short Form 36 Questionnaire; HBE: Head of Bed Elevation; Standard treatment: Based on proton pump inhibitors and/or sodium alginate, according to treating physician criteria.

WORK TEAM

Work team of this clinical trial is formed by three authors. The respective roles during the design and conduction of the trial, and also the professional profiles of each researcher are described below.

Researchers:

- [name] (Principal Researcher study design, patient recruiting, telephonic follow-up, outcome assessment, statistical analysis, writing of final report)
 - General Practice Physician Universidad Nacional de Colombia
 - 3rd year Internal Medicine resident Universidad Nacional de Colombia
- [name](Researcher patient recruiting, intervention administration, clinical and telephonic follow-up, writing of final report)
 - General Practice Physician Universidad Nacional de Colombia

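### The planned subgroup interaction test (Chi-square or Fisher, univariate relative risk) has no treatment-by-subgroup term; on its natural reading it tests prediction of response, not modification of the effect of head of bed elevation

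*Combined protocol and SAP*

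**What the plan says.** The subgroup paragraph of the Statistic analysis plan opens: "Exploratory subgroup analysis will search for differences stratified according to age group, sex, ethnic group, BMI". It continues the list through comorbidities, coffee, drug adherence, and length and severity of symptoms, "among other 16 baseline variables". Nine variables are named, so the total can be read as 16 or 25. The method is given in one sentence: "Subgroup interactions will be tested with Chi-square or Fisher exact test, and effect size was expressed as a univariate relative risk". A binomial regression is to supply that relative risk. The outcome, the rows and columns of the table and the single predictor of the relative risk are not named.

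Two binary variables elsewhere could feed this test:

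- The Primary outcome section defines effectiveness as "Change of ≥ 0,6 points between basal RDQ questionnaire and the same questionnaire administered after 6 weeks of HBE use". The control period plays no part in that definition.
- The Statistic analysis plan says that, for a complementary analysis, the score difference "between periods will be transformed into a binomial variable and a McNemar marginal homogeneity test will be applied". This variable is tied to McNemar, not to the subgroup test.

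The only model with an explicit treatment effect is the cross-over ANOVA, which lists sequence, period and treatment and no subgroup term.

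**The concern.** An interaction is a difference of differences: HBE minus control in one subgroup against HBE minus control in the other. The test needs treatment, subgroup and their product, or a within-patient treatment difference compared between subgroups. A Fisher exact option points to a simple contingency table, and a univariate relative risk has one predictor.

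If the table is responder on HBE by baseline variable, a variable that predicts improvement equally in both conditions will look like a modifier of the HBE effect. The reverse error is also possible: a real modifier whose prognostic effect runs the other way can leave the responder rates equal. Severity of symptoms is on the list. If it means baseline RDQ, it is arithmetically part of the change score.

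At stake is the labelling of exploratory findings. The Executive summary expects the trial to inform a treatment recommendation, and a predictor of improvement reported as an interaction could be carried into it.

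**Working it through.** **The plan's own figure.** No figure is given for the subgroup test, so N comes from the McNemar calculation in Table 3. Discordant pairs: 34 × 0.53782 ≈ 18. Critical value: 13. Probability of a discordant pair favouring HBE: 3.571/4.571 = 0.781. The one-sided exact binomial gives power 0.8169 and alpha 0.0481, as printed. The 34 is used below, as two subgroups of 17. Subgroup tests are two-sided at 5%, because Chi-square has no direction.

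**Reading 1: responder on HBE by subgroup.**

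*(a) The plan's improvement rates.* The Sample size section gives 58.8% with HBE and 28.6% without, a difference of 0.302.

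- No prognostic difference (58.8% in both subgroups): Chi-square flags about 5%, Fisher about 2%.
- Control rates assumed to be 38.6% and 18.6%, same risk difference: HBE rates are 0.386 + 0.302 = 68.8% and 0.186 + 0.302 = 48.8%. Chi-square flags 23%, Fisher 14%.
- Same control rates, constant odds ratio: HBE rates 69.1% and 44.9%. Chi-square flags 32%, Fisher 20%.

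*(b) RDQ scale, generic prognostic variable (simulation, 20,000 runs).* Mean improvement is 0.3 in the control period and 0.9 on HBE, so the HBE effect is 0.6 in both subgroups. A patient component and a period error, each with SD 0.7, give an SD of change of √(0.49 + 0.49) = 0.99. A shift separates the subgroups equally in both periods. Response is improvement on HBE of at least 0.6. All these values except the 0.6 threshold are assumptions.

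| Prognostic shift (RDQ points) | Responder on HBE by subgroup, Chi-square | Dichotomised within-patient difference, Chi-square | t test on within-patient difference |
|---|---|---|---|
| 0 | 5% | 6% | 5% |
| 0.5 | 21% | 6% | 5% |
| 0.8 | 46% | 6% | 5% |
| 1.0 | 63% | 6% | 5% |

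*(c) Masking.* Take a true modification of 0.6 and a prognostic shift of −0.6. On HBE they cancel (0.6 − 0.6 = 0), so responder rates match. The responder table flags 5%, the dichotomised within-patient difference 31% and the t test 41%.

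*(d) Baseline RDQ split at the median.* The SD of 1.0 is the value cited in the Sample size section. Assume correlation ρ between baseline b and follow-up, and follow-up on HBE = −0.6 + ρb + error, with no interaction. At ρ = 0.5 the responder rates are about 66% (high baseline) and 34% (low), and Chi-square flags about half of trials. For ρ from 0.7 down to 0.3, Chi-square flags 34-68% and Fisher 22-55%. The t test on the within-patient difference stays at about 5%.

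**Reading 2: HBE versus control within each stratum.** Use 58.8% and 28.6% in both strata, 17 per cell, treated as independent. The chance of significance in one stratum is p = 0.455 (Chi-square) or 0.317 (Fisher). The chance that exactly one stratum is significant is 2p(1 − p): 2 × 0.455 × 0.545 = 0.50, or 2 × 0.317 × 0.683 = 0.43. Discordant p-values would therefore appear in 43-50% of trials with no interaction at all.

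**Reading 3: dichotomised between-period difference by subgroup.** Column three of the table applies: about 6%, close to nominal. This holds if the difference is taken as HBE minus control, not second period minus first.

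**Multiplicity, a separate matter.** With independent tests at 5%: 1 − 0.95^16 = 0.56 and 1 − 0.95^25 = 0.72.

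**The case against.** The strongest reply is that the layout is inferred. The plan never says that responders are tabulated by subgroup without the control condition. It does describe a binary variable built from the difference between periods shortly before the subgroup text, and Figure 2 counts improvement both with and without HBE. If the subgroup test uses the between-period variable, the treatment contrast is built in and the test is nearly sound. This stands, and it makes the criticism conditional. It does not remove it: the between-period variable is assigned to McNemar, the stated primary outcome is defined on HBE alone, and two of the three readings do not test interaction.

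Second, splitting baseline RDQ is a worst case. The plan does not say that severity means baseline RDQ, and variables such as sex or ethnic group have no arithmetic tie to the change score. This also stands. For a variable with no prognostic value the responder table behaves properly.

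Third, the analysis is labelled exploratory and does not touch the primary outcome, McNemar test, ANOVA or sample size. That limits the weight of the point, but the label does not turn a test of prognosis into a test of interaction.

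A reader might also infer that false leads are almost certain. The figures do not support that: 56-72% is likely, not certain. It assumes independent tests of exact 5% size, and it would apply equally to valid interaction tests.

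**Conclusion.** The point holds in conditional form. The plan names a method for interaction that contains no treatment-by-subgroup term, and on the natural reading it tests whether a baseline variable predicts improvement. With 34 patients in equal subgroups and no true interaction, the Chi-square false-flag rate then runs from about 5% for a non-prognostic variable, through 21-63% for a shift of 0.5-1.0 RDQ points, to 34-68% for a median split of baseline RDQ. These rates rest on assumed prognostic strengths, an SD of change near 1.0 in the generic case, and a correlation of 0.7 to 0.3 in the baseline-split case; the documents give none of these.

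The documents do not support saying that the plan definitely tabulates HBE responders alone, or that every listed variable would be falsely flagged. The sponsor should make the change, but the trial's main conclusion does not depend on it.

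**What to change.** In the Statistic analysis plan, replace the Chi-square or Fisher interaction test with a comparison between subgroups of each patient's HBE-minus-control RDQ difference, adjusted for period. Equivalently, add a treatment-by-subgroup term to the cross-over model that already holds sequence, period and treatment. Report each interaction estimate with its 95% confidence interval, and state how many variables were tested (16 or 25). Any table of responders by baseline variable may stay if it is labelled as showing predictors of response. Keep the exploratory label, because testing this many variables produces chance findings even with a valid test.

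The cost is a change of wording and a few lines of model code on data already collected. The drawback is that, with about 34 evaluable patients, interaction intervals will be wide and fewer subgroups will reach significance.

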Sample size was estimated based on the hypothesis that HBE would produce a difference of at least 10% in RDQ and SF-36 scores. Effect size (Cohen d) was calculated as 0,49 keeping in mind an RDQ mean and standard deviation of 3,3±1,0 previously found in Spanish population with symptomatic GERD²⁴ and an SF-36 mean and standard deviation of 56,9±20,3 reported in Italian population in medical therapy with PPI²⁵. The minimally important difference selection was chosen based on the assumption that any difference smaller than 10% would have no clinical relevance. Based on this data, 14 patients per group would yield a power greater than 80% for detection of a minimally important difference as large as or larger than 0,6 points in RDQ questionnaire (range: 1 to 6) and 10 points in SF-36 questionnaire (range: 0 to 100), when using a paired t test as described in the statistical analyses plan section. Because of a complementary analysis of crossover data is planned with McNemar marginal homogeneity test, effect size was recalculated based on results of a previous trial²⁰, according to which, 58,8 % and 28,6% of placebo-treated patients in pre-omeprazole era, reported improvement of GERD symptoms with and without a HBE of 20 cm, respectively. Based on these data, and maintaining a statistical power of 80%, required sample size was adjusted to a total of 34 patients. In

figure 2, matrices for sample size calculation are shown, based on the cited trial and using internationally accepted statistical procedures²⁶. Likewise, in table 3 an output of sample size calculation is shown from G*Power 3.1.9.2 (Universität Düsseldorf, Düseldorf, Germany) software²⁷. Finally, calculated sample size was increased by 20% in order to avoid study power loss due to drop-outs or losses of follow-up. Thus, final sample size was 42 patients, 21 per group.

T test	Means: Difference between two dependent means	(matched pairs)
Analysis	A priori: Compute required sample size	
Input	Tails	One
	Effect size dz	0,4926108
	A err prob	0,05
	Power (1- β err prob)	0,8
Output	Noncentrality parameter δ	2,5596808
	Critical t	1,7056179
	Degrees of freedom	26
	Total sample size	27
	Actual power	0,8015888
McNemar	Proportions: Inequality, two dependent groups	
Analysis	A priori: Compute required sample size	
Input	Tails	One
	Odds ratio	3,571
	α	0,05
	1- β	0,8
	Prop discordant pairs	0,53782
Output	Lower critical N	13,0000000
	Upper critical N	13,0000000
	Total sample size	34
	Actual power	0,8169370

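### The plan treats an unspecified carry-over check as proof that carry-over is negligible; at 17 to 21 patients per sequence a non-significant result cannot show that, and an interval should replace it

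*Combined protocol and SAP*

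**What the plan says.** Carry-over appears in two places in the combined protocol and SAP.

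- **Follow-up:** both instruments (RDQ and SF-36) are repeated after the two-week washout. The text reads: "questionnaires will be applied again in order to be sure of the absence of any carry-over effect in the group initially allocated to HBE".
- **Statistic analysis plan:** as internal quality control, "a pre-test was applied to prove the assumption of a negligible" carry-over effect, with a reference to published guidance on cross-over trials. The next sentence says the cross-over ANOVA was used "in search for significant sequence, period and treatment effects, assuming a negligible" carry-over effect.

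Neither section names the test statistic, the contrast, a margin for what counts as negligible, an interval, or what follows if the check fails. The only significance level in the plan is general: "Differences with one-tail p<0,05 will be accepted as statistically significant". The sample size section covers the paired t test and the McNemar test, not the carry-over check.

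**The concern.** Failing to reject a null hypothesis of no carry-over is not evidence of no carry-over unless the test could have detected one that matters. Both passages nevertheless let the check settle the question, and the ANOVA is then read as free of carry-over.

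The ANOVA's sequence term gives no separate reassurance. In a 2x2 design the sequence contrast and the differential carry-over contrast are the same comparison of patient totals, so a non-significant sequence effect is the weak test under another name.

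At stake is the credibility of the HBE estimate. If benefit from the first period persisted, control scores in the second period would look better than they should, and the report could give a shrunken effect while stating that carry-over had been ruled out.

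**Working it through.** **The plan's own figures.** These reproduce.
- Paired t test: noncentrality 0.4926108 × √27 = 2.5597; with 26 df and one-tail 5%, power is 0.8016.
- McNemar: 34 × 0.53782 ≈ 18 discordant pairs; success probability 3.571/4.571 = 0.781; P(at least 13 of 18) = 0.817, actual α 0.048.
- Drop-out: 34 × 1.2 = 40.8 and 34/0.8 = 42.5, against the planned 42.

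No figure for carry-over is given, so none can be reproduced.

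**Inputs.**
- Target: a "minimally important difference as large as or larger than 0,6 points in RDQ questionnaire".
- SD: "RDQ mean and standard deviation of 3,3±1,0".
- Patients per sequence: 21 planned, or 17 if the 34 required patients complete in balance.
- Within-patient correlation ρ: not stated. The value 0.4926 is 10/20.3, which uses the between-patient SD as the SD of the difference. That implies ρ = 0.5. I use 0.3 to 0.7.

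**Size of bias.** Let τ be the HBE effect and λ the carry-over into the second-period control score of the HBE-first sequence. The period-adjusted estimate from end-of-period scores has expectation τ − λ/2. With τ = −0.6 and λ = −0.6 this is −0.6 + 0.3 = −0.3. With SD of the difference 1.0 (ρ = 0.5) and 34 completers, one-tail power falls from 96% at 0.6 to 53% at 0.3.

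**Power to detect λ = 0.6 (noncentral t).**
- Totals: SD of the sum = √(2(1+ρ)); SE = SD × √(2/n). At ρ = 0.5, n = 17: SD 1.732, SE 0.594, noncentrality 0.6/0.594 = 1.01, 32 df.
- Plain post-washout comparison: SE = √(2/n), which is 0.343 (n = 17) or 0.309 (n = 21).
- Post-washout ANCOVA on the enrolment score: SE = √(1−ρ²) × √(2/n), with 2n − 3 df.

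| RDQ check, ρ 0.3–0.7 | n = 17 | n = 21 |
|---|---|---|
| Totals, two-sided 5% | 15–18% | 18–22% |
| Totals, one-tail 5% | 24–28% | 27–32% |
| Plain post-washout, two-sided 5% | 40% | 48% |
| Plain post-washout, one-tail 5% | 53% | 61% |
| ANCOVA post-washout, two-sided 5% | 43–66% | 51–76% |
| ANCOVA 95% CI half-width | 0.50–0.67 | 0.45–0.60 |

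For the totals test at ρ = 0.5, 80% power at two-sided 5% needs about 131 per sequence. For SF-36 (carry-over 10 points, SD 20.3, ρ = 0.5), its two-sided power is 13% (n = 17) or 15% (n = 21).

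**Check by simulation.** With τ = λ = −0.6, ρ = 0.5 and 21 per sequence, 40,000 simulated trials gave a mean estimate of −0.30. The totals test rejected in 19.7%. Among trials where it did not reject, the mean estimate was still −0.30.

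**The case against.** Several points on the other side stand.

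- **The test is not named.** The totals test is conventional, but the only carry-over data the plan describes are the post-washout questionnaires. A reader might infer that carry-over of this size would usually be missed. That holds for the totals test. It does not hold for every washout-based check, since a plain comparison at one-tail 5% has 53–61% power.
- **The scenario is large.** A carry-over of 0.6 equals the whole target difference and would have to be present at week 14, eight weeks after the prisms are returned at week 6. A smaller carry-over biases less, though it is harder to detect.
- **Direction.** A reader might infer a risk of a false claim for HBE. On end-of-period scores a persisting benefit pulls the estimate toward zero, so the risk is a lost effect.
- **Outcome definition.** The primary outcome is change from a basal RDQ, and the questionnaires are repeated before period 2. If change from a period-specific baseline were analysed, the bias would be −(λ at week 14 − λ at week 8)/2. An equal carry-over at both times cancels, and a decaying one gives a different bias.
- **Error rate.** A reader might infer that a pre-test choosing the analysis distorts the type I error rate. The plan writes no such branch and calls the pre-test quality control, so the documents do not support that.
- **First-period comparison.** Specific objective 2 compares the groups in each period, and the analysis plan includes unpaired tests, so this analysis is substantially present already.
- **Sequence term.** If carry-over really is zero, the totals contrast does estimate a sequence effect, and the plan declares that assumption openly.

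None of this rescues the claim of proof. Whichever check was meant, a non-significant result would leave a material carry-over possible.

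**Conclusion.** The point holds in limited form. The plan claims to establish negligible carry-over by a check it does not specify, and no candidate check at 17–21 per sequence can support that. The power ranges assume RDQ SD 1.0, a carry-over of 0.6, and ρ between 0.3 and 0.7 where correlation enters. The 0.3 shrinkage further assumes that the carry-over lasts to the end of period 2 and that end-of-period scores are analysed.

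The documents do not show that carry-over is present. The defect is in what the plan will conclude from the check and in the missing estimate.

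**What to change.** In the statistic analysis plan and the Follow-up section:

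1. Delete the wording that the check proves, or makes sure of, the absence of carry-over.
2. Report carry-over as an estimate with 95% CI: post-washout RDQ and SF-36 compared between sequences by ANCOVA on the enrolment score. The expected RDQ half-width is about 0.45–0.67. Say that this bounds carry-over at week 8 and does not exclude it, and that it does not measure carry-over at week 14.
3. State that no carry-over test selects the treatment analysis.
4. Label the first-period between-group comparison, already implied by specific objective 2 and the unpaired tests, as the carry-over sensitivity analysis.
5. State that the ANOVA sequence term cannot be separated from carry-over.
6. State which baseline the basal score refers to in each period, since the bias depends on it.

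This needs no new patients, visits or questionnaires, only wording and a small amount of analysis on scores already collected. The downside is that the report must show an interval that may not exclude a relevant carry-over, in place of a statement that carry-over was absent.

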Cross-over: After allocation has been completed, patients in the intervention group will receive a pair of numbered wooden prisms with dimensions 20x18x18 cm along with written instructions about the correct use of the intervention. The patient must sleep with HBE during 6 weeks and both RDQ and SF-36 questionnaires will be applied again at the end of this first period while the participant is still sleeping with HBE. Afterwards, a washout 2 week period follows in which the participant sleeping with HBE will stop using it and will return the pair of wooden prisms to the researchers. After washout period has ended and both RDQ and SF-36 questionnaires have been applied again, patients allocated to the control group during the first period of the study will receive a random pair of prisms and will be instructed to use the prisms for sleeping with HBE during a second period of 6 weeks. Meanwhile, participants initially allocated to the HBE group will be followed as a control group in this second period of the study.

Blinding: Because HBE is not susceptible to double-blinding, patients allocated to the intervention group will always be aware of the group they belong to. However, the researcher in charge of statistical analysis of data and writing the results report will work with random-generated alphabetical group codes for masking the intervention in each one of the periods of the trial.

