Statistic analysis plan: Quantitative and qualitative variables collected with Basic Data Format, RDQ, SF-36 and Patient Preference questionnaires will be typed in a Microsoft Excel 2007 database. Intervention groups will be masked with an alphabetical code provided by an independent collaborator who will not be involved with data analysis or report writing. For statistical processing, database will be imported into STATA SE 13.0 for Windows (StataCorp LP, Texas, USA) and descriptive statistics will be generated for each variable. Statistically significant differences will be searched for categorical data using the Chi-square test or Fisher exact test and normality will be tested for numerical continuous variables using the Shapiro-Wilk test. For normally distributed continuous variables, statistically significant differences will be searched for by using unpaired Student's t test. Alternatively, for not normally distributed variables Mann-Whitney U test will be applied. For non-normal variables due to atypical data, values outside the percentile 50 ± 1,5 interquartile range were excluded. For complementary processing of primary outcome and secondary outcome quality of life, score difference

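### The modified intention-to-treat set omits every patient who withdrew, so it is a completer set regardless of adherence, and no missing-data method or sensitivity analysis is planned

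*Combined protocol and SAP*

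**What the plan says.** The last sentence of the Statistic analysis plan defines the modified intention-to-treat analysis. Poor adherers stay in: "participants with protocol violations because of bad adherence to HBE, were included". Patients who left do not: "it was not possible to include patients who withdrew from the study because outcome information could not be gathered completely".

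The visit schedule gives a result before the crossover. Under Cross-over, for patients starting with HBE, "both RDQ and SF-36 questionnaires will be applied again at the end of this first period". Follow-up repeats this: "At the end of the first period, RDQ and SF-36 questionnaires will be applied". Both questionnaires are applied again after washout and at week 14. The primary outcome is a change of at least 0.6 points "between basal RDQ questionnaire and the same questionnaire administered after 6 weeks of HBE use".

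The only provision for dropout is under Sample size, where the calculated number was "increased by 20% in order to avoid study power loss due to drop-outs or losses of follow-up". The Statistic analysis plan gives no imputation, no analysis using single-period data, no rule for scoring withdrawn patients as responders or non-responders, and no sensitivity analysis for missing outcomes.

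**The concern.** A reader of an intention-to-treat label expects randomised patients to be retained. Here, staying to the end decides who is analysed. Blinding states that patients using HBE always know it, and RDQ and SF-36 are the patients' own reports. Leaving may therefore depend on the condition and on how the patient feels. If so, a comparison among those who stayed can be wrong in either direction, and a larger sample does not correct it.

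The stated reason, incomplete outcome information, does not require removing the whole patient. A patient allocated to HBE first who leaves after week 6 has a baseline score and a score after 6 weeks of HBE, which is the primary outcome as defined. A patient allocated to control first who leaves at the same point has a control result only. It can contribute to a between-patient comparison in period 1 or to a mixed model. If every withdrawal came before week 6, no week 6 result is lost and only the bias question remains.

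**Working it through.** **Inputs.** From Sample size, Table 3 and Figure 2: 58.8% improve with HBE and 28.6% without; p12 = 0.4202 (improved only with HBE), p21 = 0.1177 (improved only without); odds ratio 3.571; 34 pairs, raised to 42 patients. From the Statistic analysis plan: one-sided 0.05, and McNemar mid-p when there are fewer than 25 discordant pairs. The number of withdrawals k is not given, so k = 2, 4 and 8 are assumed. The value 8 is 42 − 34, the plan's own allowance; it is neither a cap nor a forecast.

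**The plan's figure.** 34 × 0.53782 = 18.3, so 18 discordant pairs. The exact binomial critical count is 13, with alpha 0.0481 and power 0.8169, as in Table 3. Averaged over the number of discordant pairs, one-sided mid-p power with 34 completers is 0.810. If 8 of 42 leave for reasons unrelated to outcome, the planned power is roughly kept.

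**Outcome-related loss.** Let n = 42 − k. Among completers the difference is 0.588 − 0.286 = 0.302. Over all 42:

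- A, every withdrawal an HBE failure and control success: (0.302n − k)/42.
- B, every withdrawal an HBE failure, with control at its average rate: 0.588n/42 − 0.286.
- C, every withdrawal an HBE success and control failure: (0.302n + k)/42.

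For example, with k = 4: A = (11.476 − 4)/42 = 0.178; B = 0.532 − 0.286 = 0.246; C = (11.476 + 4)/42 = 0.368.

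Power is one-sided mid-p for 42 patients treated as one sample. The cell probabilities are: A, p12·n/42 and (p21·n + k)/42; B, p12·n/42 and (p21·n + 0.286k)/42; C, (p12·n + k)/42 and p21·n/42.

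| k | Completers only: power | A: points, power | B: points, power | C: points, power |
|---|---|---|---|---|
| 2 | 86% | 24.0, 68% | 27.4, 82% | 33.5, 93% |
| 4 | 85% | 17.8, 45% | 24.6, 74% | 36.8, 96% |
| 8 | 81% | 5.4, 11% | 19.0, 55% | 43.5, 99% |

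**How many withdrawals could matter in case A.** The completer table must match k.

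- k = 4: 38 completers, expected discordant pairs 38 × 0.4202 = 16.0 and 38 × 0.1177 = 4.5. At 16 v 4 the mid-p is 0.004; with four added against HBE, 16 v 8 gives 0.054.
- k = 3: 39 completers, expected 16.4 v 4.6, so 16.4 v 7.6 after the addition. Mid-p is 0.032 at 16 v 7, 0.038 at 17 v 8 and 0.054 at 16 v 8. The result depends on rounding.
- k = 8: 14 v 4 (0.010) becomes 14 v 12 (0.35).

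**What a mixed model recovers.** Assume 34 complete pairs plus 8 patients with period 1 only, four per sequence, and terms for treatment, period, sequence and a random patient effect. The standard error of the treatment effect falls by 3.4%, 2.4% and 1.4% at assumed within-patient correlations of 0.3, 0.5 and 0.7.

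**The case against.** The plan says modified, and it states the exclusion and the reason in the same sentence. That stands: nothing is concealed, and because poor adherers are kept this is not a per-protocol set. Disclosure does not, however, show how far the result depends on the patients left out.

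A reader might infer that week 6 results were in fact discarded. The documents do not show this. No withdrawal times are given. The exclusion is stated for the modified intention-to-treat analysis; the specific objectives also call for a comparison in each period, and the unpaired tests listed could use week 6 data without a second period. Whether the exclusion governs those comparisons is not stated.

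A reader might also start from 14 v 4 and conclude that three withdrawals overturn the McNemar result. That split belongs to 34 completers, with 8 of 42 already gone. With three withdrawals the answer turns on rounding.

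Case A is extreme. The cell for improvement only without HBE holds 11.8% in Figure 2, so three independent patients drawn from that table would all fall in it with probability 0.118³, about 0.2%. Cases A and C are bounds, and case B is milder.

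Finally, the 20% increase does protect power against loss unrelated to outcome. It does not protect against bias.

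**Conclusion.** The concern holds in a limited form. The analysis set is completers regardless of adherence, and the plan has neither a missing-data method nor a sensitivity analysis. A period 1 result would be lost from this analysis for any patient who withdrew after week 6.

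The size of the effect is unknown. At the plan's rates a 30.2-point difference in completers could correspond, over all 42, to between 24.0 and 33.5 points with 2 withdrawals, 17.8 and 36.8 with 4, and 5.4 and 43.5 with 8. In the worst case about 3 to 4 withdrawals bring the mid-p to about 0.05. These bounds rest on assumed withdrawal counts and on the plan's improvement rates.

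It would be tempting to read this as evidence that the HBE effect is exaggerated. The documents support no direction, because they give neither the number, the timing nor the reasons of withdrawals. The change is worth making because it is cheap and the possible effect is not negligible.

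**What to change.** Describe the current set as completers regardless of adherence, and keep that analysis. Add two sensitivity analyses:

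1. A mixed model of RDQ and SF-36 scores with treatment, period, sequence and a random patient effect, on all randomised patients with at least one end-of-period score. State the missing-at-random assumption. The gain in precision is small, and the model cannot use patients who left before week 6.
2. The responder outcome on all randomised patients. Withdrawal during a condition counts as non-response in that condition. A condition never started is filled once as response and once as non-response, and both results are shown.

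Report withdrawals by sequence, period and, where recorded, reason.

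The cost is slightly more analysis and no new visits. Because the exclusion is written in the past tense, reasons may be available only in part. The HBE effect may look less favourable or less certain, and the range from the second analysis may be wide.

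The choice of main test is a separate matter and not part of this change: Sample size relies on a paired test ("when using a paired t test as described in the statistical analyses plan section"), while the Statistic analysis plan names an unpaired one ("For normally distributed continuous variables, statistically significant differences will be searched for by using unpaired" Student's t test).
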